## Memorial Sloan-Kettering Cancer Center IRB Protocol

**IRB#: 08-123 A(8)**

14. Patients who complete five years of study treatment will undergo imaging studies as directed in Footnote 3 after every 3-6 cycles of treatment as determined by their treating physician.

15. Patients who complete five years of study treatment will return to clinic for physical exam, KPS, laboratory assessments, adverse events assessment, and concomitant medications assessment every two cycles (56 +/- 3 days).

## Memorial Sloan-Kettering Cancer Center IRB Protocol

**IRB#: 08-123 A(8)**

### 11.0 TOXICITIES/SIDE EFFECTS

Adverse events most frequently observed with Everolimus are rash, stomatitis/oral mucositis, fatigue, headache, anorexia, nausea, vomiting, and diarrhea. Infections have not been notably frequent or severe. Non-infectious pneumonitis has also been observed. The majority of these AEs have been of mild to moderate severity (CTC grade 1-2). Overall, the most frequently observed laboratory abnormalities include reduced blood counts and hyperlipidemia mostly reported as hypercholesterolemia and/or hypertriglyceridemia.

The principal DLT in Phase 1 trials has been Grade 3 stomatitis. For guidance on management of stomatitis refer to Section 9.3.1

Hyperlipidemia was reported as a serious adverse reaction. It is a recognized side-effect of rapamycins. Use of lipid-lowering drugs should be associated with dietary recommendations. Monitoring of blood lipid levels requires patients to be fasting; this aspect must be verified when interpreting results. For guidance on management of hyperlipidemia refer to Section 9.3.2.

Hyperglycemia was reported as a serious adverse reaction. Again, the fasting state of patients should be verified when interpreting results. For guidance on management of hyperglycemia refer to Section 9.3.2.

Pneumonitis is a recognized adverse effect of rapamycins (sirolimus, temsirolimus, and everolimus). Numerous case reports in the literature suggest that rapamycin-associated pneumonitis is relatively unaggressive, limited in extent, and reversible upon drug discontinuation. The term 'pneumonitis' is used here to describe radiologically evident, non-infectious, non-malignant infiltration in the lungs. More precise diagnosis should come after histocytological examination following lung biopsy, generally during bronchoscopy which may or may not be symptomatic. Advice on the management of pneumonitis has been provided in Table 5.

## Memorial Sloan-Kettering Cancer Center IRB Protocol

**IRB#: 08-123 A(8)**

treatment with Everolimus must be considered as predisposing patients to the risk of infection. This risk will be higher in patients severely immunocompromised because of their underlying disease and/or co-medications. Outcome may be fatal in case of serious infections.

A reduction in blood cell counts is frequent when Everolimus therapy is initiated. Infrequently and without clinical significance, anemia and thrombocytopenia have been reported. In heavily pretreated patients with aggressive lymphoma, the incidence of grade 3 anemia, neutropenia, and thrombocytopenia was reported to be 11%, 16%, and 30%, respectively. Serious, suspected drug-related hemorrhages have been exceptional. Nevertheless, Everolimus should be considered as predisposing patients to hemorrhage and potentially fatal should they develop severe drug-related thrombocytopenia.

Discrete, reversible changes in liver enzymes have been found to occur in numerous patients during treatment with Everolimus in oncology clinical studies and in a study in rheumatoid arthritis. In oncology studies, these changes may be evident only in patients without severe underlying morbidity. The increase in transaminases (AST and ALT) generally appears after 4 weeks of treatment. In all but a few cases it does not exceed Grade 1 ( $\leq 2.5 \times$  ULN). Similarly, mild increases in alkaline phosphatases can coexist. Spontaneous corrections or intermittent correction with continued treatment can occur. Serum bilirubin is not increased. In studies of patients with advanced cancers, clinically relevant changes in liver enzymes have been invariably associated with the presence of liver metastases and/or progression of the underlying cancer.

Renal failure has been reported in five suspected cases to date. One patient with no alternative explanation made a complete recovery following study drug adjustment and no treatment/therapy for the event. The rest of the patients had concurrent morbidities, which may have contributed to the reported events.

Reactivation of Hepatitis B (HBV) has been observed in patients with cancer receiving chemotherapy (Yeo 2004). Sporadic cases of Hepatitis B reactivation have also been seen in this setting with everolimus. Use of antivirals during anti-cancer therapy has been shown to reduce the risk of Hepatitis B virus reactivation and associated morbidity and mortality (Loomba 2008). A detailed assessment of Hepatitis B/C medical history and risk factors must be done for all patients at screening, with testing performed prior to the first dose of everolimus.

Hypophosphatemia, hypomagnesemia, hyponatremia, and hypocalcemia have been reported as serious adverse reactions. Electrolytes should be monitored in patients treated with Everolimus.

Table 4 provides general recommendations for the management of patients with suspected drug toxicities while on treatment with Everolimus as single-agent therapy.

More detailed information regarding Everolimus, reported suspected toxicities, and individual cases is provided in the [Investigator's Brochure].

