### 8.1 PRETREATMENT EVALUATION

The following will be completed within 14 days prior to initiation of treatment (unless otherwise indicated):

- Complete history and physical examination with measurements of all palpable lesions and review of all concomitant medications
- Height, weight, body surface area
- Karnofsky Performance Status
- Complete blood count (CBC) with differential and platelets
- Comprehensive panel, i.e. serum electrolytes including sodium, potassium, chloride,

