## Memorial Sloan-Kettering Cancer Center IRB Protocol

**IRB#: 08-123 A(8)**

bicarbonate, phosphorus, calcium, glucose, blood urea nitrogen, creatinine, SGOT (AST), SGPT (ALT), alkaline phosphatase, total bilirubin, total protein, albumin, and uric acid

- PT/PTT
- Fasting Lipids include triglycerides, total cholesterol, HDL and LDL
- Pregnancy test in women of childbearing age
- EKG (within 30 days)
- Baseline abdominal and pelvic CT scans or MRI for abdominal or pelvic indicator lesions (within 30 days)
- In patients with osseous lesions, bone X-rays and/or bone scans should be obtained (within 30 days)
- Chest X-ray (a CT of chest may be performed instead if clinically relevant) (within 30 days)
- Pulmonary function tests (within thirty days)
- Pre-treatment tumor tissue specimens for all patients will be analyzed using immunohistochemistry for markers including those of an activated mTOR pathway including phospho-S6 and phospho-4E BP1. Staining will be graded as 0 to 3+ (0 = 0-5%; 1+ = 6-25%; and 3+ = >50% tumor cells positive) by the Core Lab of the MSKCC Department of Pathology. The study will not require research biopsies.
- Hepatitis B testing (HBV-DNA, HBsAg, HBsAb, and HBcAb) for all patients who meet the hepatitis B risk criteria outlined in Section 6.1.

Hepatitis C testing (quantitative RNA-PCR) for all patients who meet the hepatitis C risk criteria outlined in Section 6.1.

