## Memorial Sloan-Kettering Cancer Center IRB Protocol

**IRB#: 08-123 A(8)**

**Table 4. Criteria for dose-modification in case of suspected Everolimus toxicity and re-initiation of Everolimus treatment**

Toxicity	Actions
Non-hematological toxicity	
Grade 2 (except pneumonitis – refer to Table 5)	If the toxicity is tolerable to the patient, maintain the same dose. If the toxicity is intolerable to patient, interrupt Everolimus until recovery to grade $\leq 1$ . Then reintroduce Everolimus at same dose. If event returns to grade 2, interrupt Everolimus until recovery to grade $\leq 1$ , then reintroduce Everolimus at the lower dose level.
Grade 3 (except hyperlipidemia*)(except pneumonitis – refer to Table 5)	Interrupt Everolimus until recovery to grade $\leq 1$ , then reintroduce Everolimus at the lower dose level. For pneumonitis consider the use of a short course of corticosteroids.
Grade 4 (including hyperlipidemia)	Discontinue Everolimus.
Hematological toxicity	
Grade 2 Thrombocytopenia (platelets $< 75, \geq 50 \times 10^9/L$ )	Interrupt Everolimus until recovery to grade $\leq 1$ ( $> 75 \times 10^9/L$ ), then reintroduce Everolimus at initial dose. If thrombocytopenia again returns to grade 2, interrupt Everolimus until recovery to grade $\leq 1$ . Then reintroduce Everolimus at the lower dose level.
Grade 3 Thrombocytopenia (platelets $< 50, \geq 25 \times 10^9/L$ )	Interrupt Everolimus until recovery to grade $\leq 1$ ( $\text{platelets} \geq 75 \times 10^9/L$ ). Then resume Everolimus at one dose level lower. If grade 3 thrombocytopenia recurs, discontinue Everolimus.
Grade 4 Thrombocytopenia (platelets $< 25 \times 10^9/L$ )	Discontinue Everolimus.
Grade 3 Neutropenia (neutrophils $< 1, \geq 0.5 \times 10^9/L$ )	Interrupt Everolimus until recovery to grade $\leq 1$ ( $\text{neutrophils} \geq 1.5 \times 10^9/L$ ), then resume Everolimus at the initial dose. If ANC again returns to Grade 3, hold Everolimus until the ANC $\geq 1.5 \times 10^9/L$ , then resume Everolimus dosing at the lower dose level. Discontinue patient from study therapy for a third episode of grade 3 neutropenia.
Grade 4 Neutropenia (neutrophils $< 0.5 \times 10^9/L$ )	Interrupt Everolimus until recovery to grade $\leq 1$ ( $\text{neutrophils} \geq 1.5 \times 10^9/L$ ). Then resume Everolimus at the lower dose level. If grade 3 or grade 4 neutropenia occurs despite this dose reduction, discontinue Everolimus.

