### 10.0 EVALUATION DURING TREATMENT/INTERVENTION

**Table 7. Schedule of Events**

Procedure	Screening		Cycle 1			Additional Cycles (Years 1-4)		Additional Cycles (Years 5+)		Post Treatment/ Withdrawal 	Survival Follow-up
	≤ 30 Days Prior to Dosing	≤ 14 Days Prior to Dosing	Day 1 (± 3)	Day 14 (± 3)	Day 28 (± 3)	Day 1 (± 3)	Day 28 (± 3)	Day 1 (± 3)	Day 56 (± 3)		
Informed Consent		X									
Medical History		X									
Physical Examination, KPS		X	(X) 	X		X		X 		X	
Lab Studies											
Pregnancy Test 		X									
Hematology 		X	(X) 	X		X		X 		X	
Biochemistry 		X	(X) 	X		X		X 		X	
PT/PTT		X									
Fasting Lipids 		X	(X) 			X		X 		X	
HBV-DNA, HBsAg, HBs Ab, HBs Ab, HCV-RNA-PCR 	X										
HBV DNA, HCV RNA-PCR 			X			X		X		X	
Other Assessments											
12-lead EKG	X										
Pulmonary Function Tests	X										
Disease Assessment/Tumor measurements 	X						X 		X 	X	
Adverse Events 			X	X		X		X 		X	
Concomitant Medications		X	X	X		X		X 		X	
Treatment compliance 					X		X		X		
Everolimus 			X →	→	→	→	→	→	→		
Survival Status 											X
Tumor Tissue Evaluation 	X										

(X) – if applicable    X → - start and continue treatment    → - continue treatment

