## Memorial Sloan-Kettering Cancer Center IRB Protocol

IRB#: 08-123 A(8)

Footnotes for Schedule of Events	
1. Complete blood count (CBC) with differential and platelets	
2. Comprehensive panel (i.e. serum electrolytes including sodium, potassium, chloride, bicarbonate, phosphorus, calcium, glucose, blood urea nitrogen, creatinine, SGOT (AST), SGPT (ALT), alkaline phosphatase, total bilirubin, total protein, albumin, uric acid).	
Fasting Lipids include triglycerides, total cholesterol, HDL and LDL.	
3. Disease Assessment/Tumor Measurements: Re-staging imaging studies will be performed after every two cycles of treatment (1 cycle = 4 weeks) during the first five years of treatment and after study completion or withdrawal. Imaging studies should be performed during weeks 7 or 8. The same imaging studies performed at baseline (e.g., CT or MRI) should be performed throughout the study, when possible. Baseline chest CT or chest x-ray must be performed. If chest CT or chest x-ray is not part of the disease assessment, it must be repeated every 2 months. Bone x-ray(s)/scan to be performed if bone metastases are present.	
4. Adverse Events: Patients must be followed for adverse events from the first day of study treatment until at least 28 days after the last on-study treatment administration, or until all serious or study drug-related toxicities have resolved or are determined to be "chronic" or "stable," whichever is later. Serious adverse events should be monitored and reported as described in the protocol.	
5. Post-study survival status: Follow-up survival information will be collected for all patients by clinic visit or telephone contact approximately every 6 months for up to 2 years from the date of first dose of Everolimus. Patients will be followed until disease progression and/or death.	
6. Physical Examination/Hematology/Biochemistry/Fasting Lipids: Physical Examination/ Hematology/ Biochemistry/Fasting Lipids on Cycle 1 Day 1 is not required if performed within 7 days of Day 1 unless clinically indicated.	
7. Post Treatment/Withdrawal: This visit will take place 1 month after the last dose of study drug. Patients with ongoing study drug-related toxicities should be followed as dictated in footnote 4. These patients should be followed at the interval deemed appropriate by their study physician.	

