## Memorial Sloan-Kettering Cancer Center IRB Protocol

**IRB#: 08-123 A(8)**

Frequency of toxicity will be tabulated according to the NCI Common Toxicity Criteria, version 3.0.

Biological markers including phospho-S6 and phospho-4E BP1 will be evaluated in all pre-treatment specimens. Patients will be categorized on the basis of marker levels into three categories: no expression, low expression, or high expression. These levels will be correlated with PFS using a log rank test and will be correlated with response to treatment (complete response/partial response versus no response) using Fisher's exact test..

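### Hypomagnesemia is named as a serious reaction to everolimus, but no scheduled blood test measures magnesium

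*Combined protocol and SAP*

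**What the plan says.** Section 11.0 (Toxicities/Side Effects) names four electrolyte disturbances and follows them with a general instruction: "Hypophosphatemia, hypomagnesemia, hyponatremia, and hypocalcemia have been reported as serious adverse reactions. Electrolytes should be monitored in patients treated with Everolimus". It gives neither an analyte list nor a frequency for that monitoring.

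The operative detail is elsewhere. Section 8.1 (Pretreatment Evaluation) sets out the baseline chemistry, beginning "Comprehensive panel, i.e. serum electrolytes including sodium, potassium, chloride" and continuing "bicarbonate, phosphorus, calcium, glucose, blood urea nitrogen, creatinine, SGOT (AST), SGPT (ALT), alkaline phosphatase, total bilirubin, total protein, albumin, and uric acid". Footnote 2 of the Schedule of Events in Section 10.0 defines the on-treatment panel in the same terms, starting "serum electrolytes including sodium, potassium, chloride, bicarbonate, phosphorus, calcium, glucose". The Biochemistry row of the schedule refers to that footnote.

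Two parts of the plan use the results. Section 14.0 says "Frequency of toxicity will be tabulated according to the NCI Common Toxicity Criteria, version 3.0". Table 4 in Section 9 sets grade-based actions for non-hematological toxicity; after an interruption for Grade 3, for example, the instruction is "then reintroduce Everolimus at the lower dose level".

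**The concern.** The protocol identifies a specific laboratory risk, tells investigators to monitor that class of risk, and then itemises a panel that omits one of the four analytes concerned. A site that runs the schedule exactly as written would never measure magnesium.

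Safety and toxicity is one of the two primary objectives (Section 2.0) and endpoints (Section 4.2). An asymptomatic laboratory abnormality can be graded only if a value exists. Three of the named disorders would be looked for at every biochemistry draw, while the fourth would depend on individual ordering. A low count of hypomagnesemia in the final table could then mean either that it was rare or that it was seldom tested. With no baseline value, attributing a later low result to the drug would also be harder. The Table 4 rules cannot act on a value that was never obtained.

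**Working it through.** The plan states no figure on this point, so the check sets the lists side by side and counts.

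**Step 1: count the panel.** The analytes in Section 8.1 and in footnote 2, grouped:

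- electrolytes: sodium, potassium, chloride, bicarbonate, phosphorus, calcium (6)
- glucose and renal: glucose, blood urea nitrogen, creatinine (3)
- hepatic: AST, ALT, alkaline phosphatase, total bilirubin (4)
- other: total protein, albumin, uric acid (3)

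Total: 6 + 3 + 4 + 3 = 16. Magnesium is 0 of 16, in both lists.

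**Step 2: match the Section 11.0 disorders to the panel.**

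| Disorder named in Section 11.0 | Analyte needed | In Section 8.1 | In footnote 2 |
|---|---|---|---|
| Hypophosphatemia | Phosphorus | Yes | Yes |
| Hypomagnesemia | Magnesium | No | No |
| Hyponatremia | Sodium | Yes | Yes |
| Hypocalcemia | Calcium | Yes | Yes |

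Three of four are covered.

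**Step 3: look for another route.** The other laboratory rows of the Schedule of Events are hematology, PT/PTT, fasting lipids, pregnancy and hepatitis tests. None includes magnesium. Section 9 requires at least weekly follow-up of drug-related abnormal laboratory values that led to interruption or discontinuation. That applies once an abnormality is known and does not create the first test.

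**Step 4: count the draws that could carry it.** For a patient who reaches Cycle 2, biochemistry is scheduled at screening, Cycle 1 Day 1 (waived under footnote 6 if done within the previous 7 days), Cycle 1 Day 14 and Cycle 2 Day 1.

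- With the waiver: 1 + 0 + 1 + 1 = 3
- Without it: 1 + 1 + 1 + 1 = 4

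Added tests through Cycle 2:

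- 37 patients: 37 × 3 = 111 to 37 × 4 = 148
- 23 patients (stop after Stage 1): 23 × 3 = 69 to 23 × 4 = 92

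These totals exclude later cycles and the post-treatment visit. A patient who starts *k* cycles within the first five years and attends the post-treatment visit has 1 (screening) + 0 or 1 (Cycle 1 Day 1) + 1 (Day 14) + (*k* − 1) + 1 (post-treatment) = *k* + 2 to *k* + 3 draws.

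**Step 5: see where Table 4 would bite.** It lists no action for Grade 1 non-hematological toxicity, and a tolerable Grade 2 event keeps the same dose. Grade 3 calls for interruption and a lower dose, and Grade 4 for discontinuation. For an asymptomatic patient, an unmeasured magnesium therefore changes dosing only at Grade 3 or 4.

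**The case against.** The strongest reply is that monitoring is not left wholly to choice. The instruction in Section 11.0 directly follows the sentence naming hypomagnesemia, so in context it covers magnesium, and the word *including* leaves the panel open. This is fair as far as it goes: the protocol permits the test and encourages it. But it does not schedule it. Both lists are introduced by *i.e.* and run down to uric acid, and neither the instruction nor the lists set a time for a magnesium measurement.

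A second reply is that little depends on it. The toxicity analysis is a descriptive single-arm tabulation, and Section 14.0 has no toxicity stopping rule. Symptomatic and serious cases reach the record through adverse event and SAE reporting. Asymptomatic Grade 1 or tolerable Grade 2 values would change no dose even if measured. All of this stands, and it is why the point is minor. It does not remove the uneven ascertainment among the four electrolytes or the missed dose action at Grade 3 or 4.

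Third, the draw counts do not fit every patient. Section 14.0 anticipates that some will stop after one cycle or less; they may miss Cycle 2 Day 1 and have the post-treatment draw instead. The totals are approximate. Because patients inevaluable for the primary endpoint remain evaluable for toxicity, the number tested could also somewhat exceed 37.

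**Conclusion.** The concern holds as a minor point. Of the four electrolyte reactions that the protocol calls serious, three are measured at every scheduled biochemistry draw and magnesium at none, including baseline. Asymptomatic hypomagnesemia would be under-ascertained for the safety objective, and an asymptomatic Grade 3 or 4 value could go without the dose action Table 4 requires.

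The number of missed cases cannot be estimated, because the documents give no frequency of hypomagnesemia and no indication of how often sites would order the test unprompted. The progression-free survival decision rule, sample size and error rates are unaffected.

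The conclusion assumes that the itemised lists define what is run as the scheduled panel. Part of Section 11.0 was not available to check, nor was the Investigator's Brochure; the two panel lists and the schedule, which govern testing, were.

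**What to change.** Add serum magnesium to the comprehensive panel in Section 8.1 and in footnote 2 of the Schedule of Events. The existing Biochemistry row then carries it at screening, Cycle 1 Day 1 where applicable, Cycle 1 Day 14, Day 1 of each further cycle (every two cycles after five years) and the post-treatment visit. Section 14.0 needs no change.

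The cost is one more analyte on blood already drawn, with no new visit or procedure, in the numbers given above. Some incidental low-grade findings will need follow-up. Section 16.4 lists the addition of a safety-monitoring test among changes needing IRB approval, so a written amendment is required. The benefit goes to patients still to be enrolled or still on treatment.

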## Memorial Sloan-Kettering Cancer Center IRB Protocol

IRB#: 08-123 A(8)

### 12.1 CRITERIA FOR THERAPEUTIC RESPONSE/OUTCOME ASSESSMENT

Response and progression will be evaluated in this study using the international criteria by the Response Evaluation Criteria in Solid Tumors (RECIST) Committee [JNCI, 92(3):205-216, 2000]. Changes in the largest diameter (uni-dimensional measurement) are used in the RECIST criteria. Note: lesions are either measurable or non-measurable using the criteria provided below:

#### 12.2 Definitions

Measurable lesions: lesions that can be accurately measured in at least one dimension with longest diameter  $\geq$  20 mm using conventional techniques or  $\geq$  10 mm with spiral CT scan.

Non-measurable lesions: all other lesions (or sites of disease) including small lesions (longest diameter  $<$  20 mm with conventional techniques or  $<$  10 mm using spiral CT scan) are considered non-measurable disease. Bone lesions, leptomeningeal disease, ascites, pleural/pericardial effusions, lymphangitis cutis/pulmonis, inflammatory breast disease, abdominal masses (not followed by CT or MRI), and cystic lesions are all non-measurable.

Target lesions: all measurable lesions – up to a maximum of five lesions per organ and 10 lesions in total, representative of all involved organs – should be identified as target lesions and recorded and measured at baseline. Target lesions should be selected on the basis of their size (lesions with the longest diameter) and their suitability for accurate repeated measurements (either by imaging techniques or clinically). A sum of the longest diameter (LD) for all target lesions will be calculated and reported as the baseline sum LD. The baseline sum LD will be used as reference by which to characterize the objective tumor response.

Non-target lesions: all other lesions (or sites of disease) should be identified as *non-target lesions* and should also be recorded at baseline. Measurements of these lesions are not required, but the presence or absence of each should be noted throughout follow-up.

